Figure 1. Image of post-anesthesia care unit bay in Barnes-Jewish Hospital with two-way video communication.

A station in our telemedicine center will be designated for monitoring patients assigned to the two PACU bays during this proof-of-concept study. Patient information flows to the telemedicine center through the electronic health record (EHR), physiological waveform tracings, and direct video observation. A version of AlertWatch® (AlertWatch, Ann Arbor, Michigan) decision-support software, customized for the PACU environment (Figure 2), will assist clinicians in the telemedicine center in performing core PACU-related functions remotely (see *Aim 1*).

[figure not shown]

Figure 2. AlertWatch® decision-support software, customized for the PACU environment.

Aim 1 – Demonstrate the potential utility of a telemedicine center for the PACU, to assist with PACU functions

The assessments in relation to PACU functions will include:

- 1a. Detection of physiological derangements in PACU patients
- 1b. Identification of symptoms requiring treatment in PACU patients
- 1c. Recognition of situations requiring emergency medical intervention
- 1d. Determination of patient readiness for PACU discharge
- 1e. Participate meaningfully in hand-off activities

Observation Phase (3 months)

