In the first three months (the Observation phase) of this proof-of-concept study, a telemedicine center for the PACU will monitor patients assigned to two PACU bays. Both the telemedicine center and nurses caring for patients in the PACU bays will separately document physiological derangements (Table 2), treatable symptoms (Table 3), or a situation requiring urgent medical intervention (telemedicine center only; Table 4) during the PACU stay. Clinicians in the telemedicine center will assess when the patient meets discharge criteria, based on the modified Aldrete scale¹⁵ and their clinical judgment. They will document the time that discharge criteria are met, the modified Aldrete scale score at this time, and any additional relevant information. If clinicians in the telemedicine center judge that they are unable to determine a patient's readiness for discharge, they will document their reasons (Table 5). Clinical judgment will be used in determining appropriate discharge parameters for patients with pre-existing conditions. The telemedicine center clinicians will document each patient's information outlined in Tables 2-5 directly into REDCapTM (a secure web application for managing online surveys and databases) and AlertWatch. After a patient has been discharged from the PACU, the PACU nurse will fill out a form providing information outlined in Tables 2-5. This includes

information on physiological derangements, treatable symptoms, and discharge information. This form will be collected by the research team, and the information in the form will be documented in REDCap. During this phase of the study, clinicians in the telemedicine center will not communicate with clinicians in the PACU (nurses or physicians), unless there is a patient safety event.

Table 2. Physiological derangements and complications

Did the patient have any of the following physiological derangements:	Definition: (for study purposes)
Persistent confusion / delirium	
Tachycardia	HR >120/min
Bradycardia	HR <45/min
New onset atrial fibrillation	
Respiratory depression	<8 respirations per minute
Hypoxemia	<90% O ₂ Saturation
Hypotension	MAP <55
Weakness	<5/5 power in limbs
Emesis / vomiting	
Hyperglycemia	Glucose >200mg/dL
Hypothermia	Temperature < 35.5 C
Low urine output (for PACU stay >4h)	<0.5 ml/kg per hour

Table 3. Symptoms requiring treatment

Did the patient complain of the following symptoms:	
Dizziness or lightheadedness	Difficulty breathing
Nausea	Shivering

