Physiological derangements – Success will be measured (in the observation phase) by the ability of the telemedicine center clinicians to identify physiological derangements as they are occurring in the PACU. The extent to which the telemedicine center clinicians can identify these physiological derangements will be measured by comparing PACU nurse and telemedicine center assessment surveys for each patient (Figure 3).

Symptom identification and management – Success will be measured (in the observation phase) by the ability of the telemedicine center clinicians to identify treatable symptoms as they arise in the PACU. The extent to which the telemedicine center clinicians can identify these treatable symptoms will be measured by comparing PACU nurse and telemedicine center assessment surveys for each patient (Figure 3).

Emergency situations – Success will be measured (in the observation phase) by the ability of the telemedicine center clinicians to identify situations requiring emergency medical intervention as they are occurring in the PACU. By construction, any time the telemedicine center feels that an emergency situation is present, preserving patient safety mandates contacting the bedside clinician.

During each such contact, the telemedicine center clinician will ask if the PACU nurse was already aware of the situation, disagreed with the assessment, and had already spoken to the supervising physician regarding it. The occurrence of emergency medical situations will be extracted from the electronic health record, and the agreement between telemedicine center and PACU nurse assessments will be quantitated.

PACU discharge – Success will be measured by the ability of the telemedicine center clinicians to identify when patients are ready for discharge (observation phase [without communication] and interaction phase [active communication with patient and PACU clinicians]) (Figure 3). The impact of the telemedicine center on this key function will be examined based on feedback from key stakeholder focus groups (interaction phase; see *Aim 2*). The difference between sign-out times in the observation and the interaction phases will be compared.

Data collection methods and measures during the interaction phase

Aim 1: Demonstrate the potential utility of a telemedicine center for the PACU, to assist with PACU functions

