The accuracy of physiologic, symptom, and status assessments is less straightforward to analyze. At the heart of the proposal is the belief that telemedicine assistance will detect some abnormalities not caught (or caught later) by the bedside team and detect that the patient has adequate status for PACU discharge before the bedside nurse. Using the bedside assessment as a gold standard is therefore limited. Similarly, although we believe that abnormalities detected by either bedside or telemedicine are unlikely to be false positives, we have no way of assuring that. We also cannot reliably determine the timing of the bedside nurse's detection of an abnormality, as they may document it much later if they believe it does not require an immediate intervention.

Each status assessment event can occur multiple times for each patient; however, we are unlikely to accurately capture the bedside nurse's impression of the number of times an event occurred. We will therefore binarize the presence of each assessment type and display confusion matrices (count tabulations) for each assessment type, which we will summarize with Jaccard indices. The "null hypothesis" that these measures do not agree at all is not meaningful or the subject of this study. As described above, neither is a directional superiority hypothesis possible to evaluate. Final Aldrete scores will be assessed with pearson correlation, and a t-test of the difference in scores presented. Differences in ready-for-discharge times will be summarized as mean and standard deviation, with the null hypothesis of zero mean tested by t-test with a robust standard error.

Agreement of emergency medical status is unlikely to have enough events to be statistically compared. We will present cross-tabulations of (emergency detected by telemedicine center:

yes/no) and (PACU nurse: disagree, investigate and agree, already aware, physician contacted). The absolute rate of telemedicine center false positives (team disagrees), true positives (team unaware), true positives (team aware), and false negatives (team aware > 15 minutes prior or t never detects) will be presented with 95% confidence intervals.

Data Collection

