Multiple sources will be utilized for data collection from which outcome measures will be extracted. Data from AlertWatch will be automatically logged to a secure database. Preoperative patient characteristics, comorbidities, surgical and clinical history, as well as perianesthesia information will be captured using Epic Systems software (Verona, WI, USA). Prospective data will be collected from Epic Systems for the datapoints mentioned throughout the proof-of-concept study.

Relevant PACU information outlined in Tables 2-5 for patients in this study will be collected and entered into a REDCap database managed by Washington University. Data will not be shared with others outside the research team.

Methodological strengths and limitations

A strength of this study is its pragmatic approach as a real-world study with measurable aims. Feasibility will be determined, and information will be provided regarding logistical implications of establishing a telemedicine solution for the PACU. Many telemedicine solutions have been implemented without considering barriers and facilitators, such as cultural and political obstacles. This study proactively addresses these concerns, which might facilitate future successful implementation and generalization of similar telemedicine initiatives. Specific

functions of the PACU have been detailed, and the methods of this study will allow assessment of the ability of the telemedicine center to facilitate the accomplishment of these functions. This study also has important limitations. First, as a proof-of-concept, it will only include two PACU bays. Thus, its applicability to a large PACU will not be resolved. Second, PACU clinicians will be aware of the initiative, which could modify their behavior during the conduct of the study. Third, as the study design is observational with a before and after approach, improvements (for example in time to discharge) cannot be causally attributed to the intervention; there could be confounding explanations. Fourth, the current discharge criteria for the PACU do not have a firm evidential foundation (there is no gold standard measure for discharge readiness), and clinician gestalt plays an important role. This limitation can be addressed through development of rigorous, reliable and practical criteria. Finally, as a single center study, results will not necessarily be broadly generalizable.

Adverse Events and Safety Monitoring

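### Aim 1a: up to 8 of the 12 Table 2 derangements could be checked against recorded values, which the planned nurse-versus-telemedicine agreement cannot replace

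*Combined protocol and SAP*

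**What the plan says.** Under Statistical Methods, Secondary Outcomes, the plan introduces the topic with "The accuracy of physiologic, symptom, and status assessments is less straightforward to analyze". It calls the bedside assessment a limited gold standard and adds that "although we believe that abnormalities detected by either bedside or telemedicine are unlikely to be false positives, we have no way of assuring that". The analysis will then "binarize the presence of each assessment type and display confusion matrices (count tabulations) for each assessment type, which we will summarize with Jaccard indices". The same text rules out a directional superiority hypothesis.

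The success measures at the end of the Interaction Phase section, which for derangements apply to the observation phase, match this: "The extent to which the telemedicine center clinicians can identify these physiological derangements will be measured by comparing PACU nurse and telemedicine center assessment surveys". No third source enters the comparison.

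Table 2 gives many of the derangements a numeric definition, for example "<8 respirations per minute" and "Glucose >200mg/dL". On data sources, the Primary Intervention section says "Patient information flows to the telemedicine center through the electronic health record (EHR), physiological waveform tracings, and direct video observation", and Data Collection says "Data from AlertWatch will be automatically logged to a secure database" and provides for prospective collection from Epic. For emergencies, the plan already takes occurrence from the electronic record.

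**The concern.** Aim 1a asks whether telemedicine detects derangements, and the stated rationale is that it will catch some that the bedside team misses. The evidence for that lies in the discordant cells of the nurse-versus-telemedicine table. Without a reference outside the two reports, a telemedicine-only call may be a real event the nurse missed or a false alarm, and the analysis cannot tell which. Events that both teams missed fall unseen into the neither cell.

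For an item defined by a number, whether a recorded value crossed that number can be looked up. The plan names sources in which such values may be held but never compares them with Table 2. The study could then finish with an agreement index that is compatible with opposite conclusions about its central idea.

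**Working it through.** The documents give no sample size, power or precision for Aim 1a, so there is no planned figure to reproduce.

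**1. Table 2 items by type of definition (12 rows)**

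- Threshold on a monitor-type signal: tachycardia, bradycardia, respiratory depression, hypoxemia, hypotension = 5.
- Threshold on an intermittent or charted measurement: hyperglycemia, hypothermia, low urine output = 3.
- Graded bedside examination: weakness = 1. It is numeric in form but is not a recorded reading, so it is not counted.
- No definition given: confusion/delirium, new atrial fibrillation, emesis = 3.

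Measured thresholds: 5 + 3 = 8 of 12. The remaining four have no recorded-value reference of this kind.

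**2. What the Jaccard index can show**

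The documents give no event rates, so the table for 250 observation-phase patients is assumed: both teams a = 10, telemedicine only b = 10, nurse only c = 5, neither 225. All positives other than the telemedicine-only calls are taken as true, with no event missed by both teams.

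J = a/(a + b + c) = 10/25 = 0.40.

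- *All 10 telemedicine-only calls true.* True events = 10 + 10 + 5 = 25. Telemedicine PPV = 20/20 = 100%, sensitivity = 20/25 = 80%. Nurse sensitivity = 15/25 = 60%.
- *Five of the 10 true.* True events = 20. Telemedicine PPV = 15/20 = 75%, sensitivity = 15/20 = 75%. Nurse sensitivity = 15/20 = 75%.
- *All 10 false.* True events = 15. Telemedicine PPV = 10/20 = 50%, sensitivity = 10/15 = 67%. Nurse sensitivity = 15/15 = 100%.

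J stays at 0.40 throughout, while the more sensitive team changes from telemedicine to the nurse. The full confusion matrix is also identical in all three cases.

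**3. Precision a reference would give**

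Assume event rates of 2%, 5%, 10% and 20% in 250 patients, about 80% detection, and a recorded value for every patient. The Wilson 95% interval is

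[p + z²/2n ± z√(p(1−p)/n + z²/4n²)] / (1 + z²/n), with z = 1.96.

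For 20 of 25: (0.8 + 0.0768 ± 1.96 × √(0.0064 + 0.0015)) / 1.1537 = 0.760 ± 0.151, or 61% to 91%.

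- 4 of 5 detected: 38% to 96%
- 10 of 12: 55% to 95%
- 20 of 25: 61% to 91%
- 40 of 50: 67% to 89%

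The intervals are useful for common items and weak for rare ones.

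**4. How many patients can be assessed**

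Table 2 applies low urine output only to stays over 4 hours. The plan gives time to discharge suitability as mean 150, SD 65 min. Taking that as a rough stand-in for stay and assuming normality, (240 − 150)/65 = 1.38, an upper tail of about 8%, or about 21 of 250 patients. Actual stays are longer and probably skewed, so this is only indicative, but it shows why the number assessable must be reported for each item.

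**The case against.** The strongest reply is that the reference is less available and less neutral than it looks. Most of it stands.

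- **Retention.** The plan says AlertWatch data are logged but not what the log holds. Clinicians enter their own assessments there, so it might contain entries or alerts and not vital signs. The waveform sentence describes a live feed, not storage. Epic collection is stated, but no vital-sign extraction or sampling interval is given.
- **Coverage.** A reader might infer that 8 of 12 items (67%) can be adjudicated from stored data. The documents do not support that: glucose, temperature and urine output can be classified only where someone measured and charted them.
- **Independence.** Telemedicine works from the same feed that would supply the reference, whereas the nurse form is completed after the patient leaves the unit. A crossing absent from the form does not prove the nurse missed it. A reader might infer that a paired McNemar test of superiority becomes available; it would partly measure access to the feed and recall on the form.
- **Scope.** The plan's caution also covers symptoms and status. It is fair there, as it is for the four other Table 2 items. The timing of nurse detection also stays unknown.
- **Artefact.** Table 2 sets no duration or repeat-reading rule, so a single crossing is not an error-free truth.

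These limits call for a descriptive check with stated caveats. They do not justify having no check, since the planned table leaves its discordant cells uninterpretable and the plan already uses the electronic record for emergencies.

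**Conclusion.** The concern holds in a limited form. Saying there is no way to check false positives is too broad for up to 8 of the 12 derangements: five on monitor-type signals, and three where a value was measured and charted. The planned agreement summary cannot show whether telemedicine finds real derangements that the bedside team misses; in the assumed table, J = 0.40 fits a telemedicine PPV anywhere from 50% to 100%.

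This rests on time-stamped values being retrievable from Epic or the AlertWatch log, which the documents make plausible but do not confirm. It would go too far to say agreement tells nothing about Aim 1a, because concordance is partial evidence that telemedicine can identify derangements. The point concerns a descriptive secondary analysis in a two-bay proof-of-concept study and leaves the primary outcome untouched. It is a cheap improvement worth making.

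**What to change.** 1. State which time-stamped values are retained in Epic and in the AlertWatch log, item by item.
2. For observation-phase patients with recorded values, pre-specify a reference for each of the eight items before the agreement data are examined: any value past the Table 2 threshold, and a sustained version with a written persistence and artefact rule.
3. Beside the confusion matrices, report each team's sensitivity and PPV with 95% CI, the number of patients assessable per item, and the threshold events that neither team reported. Keep this descriptive, with no McNemar or other superiority test.
4. State the limitations: the shared data feed and the later nurse form may favour telemedicine, intervals will be wide for rare items, and some artefact will remain.
5. Keep the agreement-only summary for symptoms and for delirium, atrial fibrillation, weakness and emesis, and confine the remark about false positives to assessments without a recorded reference.

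If the values are retained, the cost is modest programming and a few sentences in the plan, with no new patient contact. If they are not retained for an item, saying so is enough.

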Severe pain (Numerical Rating Scale >7/10)	Itching
Chest pain unrelated to surgery	

Table 4. Emergency medical interventions

Did the telemedicine center contact PACU clinicians for any of the following interventions:	
Intubation	Unplanned transfusion
Assisted ventilation	Naloxone administration
Cardiopulmonary resuscitation	Return to OR
Cardioversion	Other (free text box)
If Yes, please check all that apply:	
 PACU nurse already aware of the situation	
 PACU nurse unaware of the situation	
 PACU nurse disagreed with the assessment	
 PACU nurse had already spoken to the supervising physician regarding the situation	

Other (please describe):

*Only the telemedicine center will document the detection of urgent situations.

Table 5. Patient discharge readiness

At what time did the patient sufficiently recover to be discharged (case attending anesthesiologist contacted for discharge)?	
PACU Nurses	Telemedicine Center for PACU
Time anesthesiologist is contacted for discharge evaluation	Time ready for discharge
Aldrete Score at discharge	Aldrete Score at discharge
	Unable to determine patient's readiness for discharge
Modified Aldrete Scale Component and Scoring Parameters	If Unable to fully assess, select reason(s) why (Checkbox)
Respiration	 More patient information needed  Equipment issues  Patient cooperation  Other (free text box)
2 – Able to take deep breath and cough	
1 – Dyspnea / Shallow Breathing	
0 – Apnea	
O₂ Saturation	
2 – Maintains > 92% on room air	
1 – Needs O ₂ inhalation to maintain O ₂ saturation > 90%	
0 – Saturation <90% even with supplemental O ₂	
Consciousness	
2 – Fully awake	
1 – Arousable on calling	
0 – Not responding	
Circulation	
2 – BP ± 20mmHg pre-op	
1 – BP ± 20-50mmHg pre-op	
0 – BP ± greater than 50mmHg pre-op	
Motor Activity	
2 – Able to move 4 extremities voluntarily or on command	
1 – Able to move 2 extremities voluntarily or on command	
0 – Able to move 0 extremities voluntarily or on command	

Interaction Phase (3 months)

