We will conduct focus groups with stakeholders to gain insights regarding their perceptions of barriers and facilitators related to the above-noted PACU functions before and after the implementation and use of a telemedicine center for the PACU. We will also gather perspectives from the stakeholders on the role and impact of the telemedicine center on their individual and team workflows in the PACU and between units during care transitions. Focus group participants will include nurses, anesthesiologists, surgeons, hospital administrators, and PACU telemedicine center clinicians. Our focus groups will be homogeneous in order to understand the clinician workflow based on their professional role, and their use of the telemedicine center in supporting their role and responsibilities. Each focus group will comprise five to six participants. This will allow in-depth discussions of the workflow problems and unintended

consequences caused by the implementation and use of the telemedicine center for the PACU. The focus group sessions will be guided by a semi-structured interview guide focused on the following themes: (1) PACU core functions, (2) PACU patient workflow, (3) PACU clinician activities and tasks, (4) tools and technologies used to support the PACU workflow, (5) major barriers to PACU functions, (6) use of a telemedicine intervention as a potential mechanism to support effective and efficient functioning of the PACU. We plan to conduct 6-8 focus group sessions (4 pre-intervention during observation phase, and 4 post-intervention during interaction phase) or until data saturation is attained.

Study Size

Patients are allocated to PACU bays according to the discretion of the nurse in charge of the PACU. Currently, approximately two patients per day are cared for in each bay in the participating PACU. Therefore, the telemedicine team will monitor approximately four patients per day over the course of the proof-of-concept study. We estimate that 500 patients will be included in this proof-of-concept study (250 per monitored phase) (Figure 4).

[figure not shown]

Figure 4. Allocation of sample size and PACU layout for proof-of-concept study

Statistical Methods

Primary Outcome

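### If final Aldrete scores sit near the ceiling, Pearson correlation and a t-test together cannot tell close agreement between nurse and telemedicine center from poor, cancelling disagreement

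*Combined protocol and SAP*

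**What the plan says.** Under Statistical Methods, Secondary Outcomes, the whole plan for this comparison is one sentence: "Final Aldrete scores will be assessed with pearson correlation, and a t-test of the difference in scores presented". No measure of agreement is named for these scores. For the binarized physiologic, symptom and status assessments, the same section says it will "display confusion matrices (count tabulations) for each assessment type, which we will summarize with Jaccard indices". It also says there that the null hypothesis "that these measures do not agree at all is not meaningful or the subject of this study".

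The scores come from Table 5, where the nurse column and the telemedicine column each carry the entry "Aldrete Score at discharge". The scale in Table 5 has five components scored 0 to 2, so totals are whole numbers from 0 to 10.

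On timing, the Observation Phase section says: "Clinicians in the telemedicine center will assess when the patient meets discharge criteria, based on the modified Aldrete scale", together with their clinical judgment. It continues: "They will document the time that discharge criteria are met, the modified Aldrete scale score at this time, and any additional relevant information". The nurse fills out a form after the patient has left the PACU. Study Size expects about 250 patients per phase, so at most about 250 pairs of scores per phase.

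**The concern.** Aim 1 includes whether telemedicine clinicians can determine readiness for discharge, and the Aldrete scale guides that judgment. The useful result is how often the remote and bedside scores match in the same patient, and by how much they differ when they do not. Pearson correlation answers another question: whether patients scored higher by one rater are also scored higher by the other. That depends heavily on how far scores spread between patients. The t-test looks only at the mean difference, so a patient scored one point higher remotely cancels one scored a point lower.

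The scale helps to decide when the score is taken, so a narrow spread near 10 is likely. Correlation then rests on the few patients scored below 10. A low r could be read as poor concordance when the raters nearly always agree, and the t-test beside it would not correct that reading.

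**Working it through.** **Inputs.** The documents state no expected correlation, agreement target or power for this comparison, so there is no figure of the plan's own to reproduce. From the documents: integer scores 0 to 10 (Table 5) and n = 250 (Study Size, one phase). Assumed: the score distributions and the level of agreement, which the documents do not give.

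**1. High agreement at the ceiling.** Let all scores be 9 or 10. Fix 12 discordant pairs, 6 in each direction, so exact agreement is 238/250 = 95.2%. Let k patients be scored 9 by both raters. Each rater then gives a 9 to a fraction p = (k + 6)/250, and

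r = (k/250 − p²) / [p(1 − p)].

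For k = 0: p = 0.024 and r = −0.024²/(0.024 × 0.976) = −0.025. For k = 50: p = 0.224 and r = (0.200 − 0.0502)/(0.224 × 0.776) = 0.86.

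| Patients scored 9 by both (k) | Exact agreement | r |
|---|---|---|
| 0 | 95.2% | −0.025 |
| 1 | 95.2% | 0.12 |
| 2 | 95.2% | 0.23 |
| 5 | 95.2% | 0.43 |
| 10 | 95.2% | 0.60 |
| 25 | 95.2% | 0.78 |
| 50 | 95.2% | 0.86 |

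In every row the mean difference is 0, t = 0, and the SD of the differences is √(12/249) = 0.22. Agreement is constant while r moves across most of its positive range.

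**2. Poor, symmetric disagreement.** Let scores run from 8 to 10, with this table (rows one rater, columns the other):

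| | 8 | 9 | 10 |
|---|---|---|---|
| 8 | 10 | 20 | 20 |
| 9 | 20 | 50 | 30 |
| 10 | 20 | 30 | 50 |

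Exact agreement is (10 + 50 + 50)/250 = 44%. Both raters have mean 9.2 and variance 0.56, and the covariance is 0.04, so r = 0.04/0.56 = 0.07 (p = 0.26). The mean difference is 0 and t = 0. The SD of the differences is √[(100 × 1² + 40 × 2²)/249] = 1.02.

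**3. Side by side.**

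| | Step 1, k = 0 | Step 2 |
|---|---|---|
| Pearson r | −0.025 (p = 0.70) | 0.07 (p = 0.26) |
| t | 0 | 0 |
| Exact agreement | 95.2% | 44% |
| Within one point | 100% | 84% |
| 95% limits of agreement (±1.96 SD) | −0.43 to 0.43 | −2.00 to 2.00 |

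The two planned statistics give nearly the same answer for very different tables. The direct measures separate them. The Wilson 95% interval for 238/250 is 91.8% to 97.2%.

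**4. Two further cases.** If one rater is always a point lower, with scores from 7 to 10, r = 1.00 with 0% exact agreement; the mean difference of 1 shows the shift. If one rater gives everyone 10 and the other gives 10 patients a 9, exact agreement is 240/250 = 96% and r is undefined. The t-test then gives p = 0.001 for a mean difference of 10/250 = 0.04 points.

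**5. Would kappa do better?** Suppose each rater gives 10 in 95% of patients, otherwise 9, and they agree in 92%. The discordant 8% splits 4% each way, so both give 10 in 91% and both give 9 in 1%. Then r = (0.91 × 0.01 − 0.04²)/(0.95 × 0.05) = 0.158. Agreement expected by chance is 0.95² + 0.05² = 0.905, so kappa = (0.92 − 0.905)/(1 − 0.905) = 0.158, the same value. In step 1 with k = 0, weighted kappa and the concordance correlation coefficient are both −0.025, equal to r.

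**The case against.** The strongest defence is that the correlation and the t-test are presented together. A reader might infer that the study could report good concordance while one rater is consistently lower, or while disagreements cancel. The documents do not support that. A constant shift leaves r high but appears in the mean difference, and in the cancelling example r falls to 0.07, which nobody would call good concordance. What remains is narrower: both results are uninformative when high agreement at the ceiling and symmetric disagreement look alike. A reported SD or confidence interval for the difference would help to separate them, but the plan specifies a mean and standard deviation only for the discharge-readiness times, not for the scores.

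A second objection is that the ceiling is not documented. This stands as a caveat. No threshold or distribution is given, clinical judgment also enters, and Table 5 gives 1 rather than 2 for needing oxygen or for a blood pressure 20 to 50 mmHg from baseline, so totals below 10 at discharge are possible. A reader might infer that r will be near zero; the documents support only that it could be.

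Third, a reader might take every mismatch as rater error. The telemedicine score is tied to the moment criteria are met and the nurse's to discharge, and the plan expects the telemedicine center to recognise readiness earlier. Some differences may therefore reflect recovery between the two times.

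Finally, this is one secondary summary in a proof-of-concept study with no decision rule attached. That limits the importance of the point but does not make the summary suitable.

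**Conclusion.** The point holds in a limited form. The plan has no measure of patient-level agreement for final Aldrete scores, and its two statistics together cannot separate very good agreement at the ceiling (95.2% exact, r = −0.025, t = 0) from poor, cancelling disagreement (44% exact, r = 0.07, t = 0). At the same 95.2% agreement, r can lie anywhere from about −0.03 to 0.86. These sizes rest on assumed tables of 250 patients and on a restricted score range, which is a strong inference from when and how the score is taken but is not stated. The matter is minor: it concerns a secondary comparison only.

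**What to change.** Replace Pearson correlation as the lead summary in Secondary Outcomes with:

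- the full cross-tabulation of paired nurse and telemedicine scores, in line with the count tables already planned for the binarized assessments;
- percent exact and percent within-one-point agreement, each with a 95% confidence interval (the second is 100% by construction if only 9s and 10s occur);
- the mean paired difference with 95% limits of agreement, read beside the cross-tabulation because the scores are whole numbers with a ceiling.

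Any weighted kappa or concordance coefficient should be secondary, with a note that it shares the ceiling problem. Making it the lead would reproduce the difficulty.

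State which two scores are paired, and report the time between them.

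Both scores are already collected, so the cost is a change of wording in the analysis plan. Sample size and primary analysis are unchanged.
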